# Background

Epidural analgesia is the most effective form of pain relief for women in labour. However, epidural analgesia is associated with an increased risk of C-section, instrumental vaginal delivery (IVD), and perineal trauma requiring surgical repair. There has been interest in position during second stage of labour for women with an epidural, in order to prevent instrumental deliveries and increase the number of spontaneous vaginal delivery (SVD). However, this issue has so far not been adequately addressed. The longer-term impacts of IVD/C-sections are profound and can include urinary and faecal incontinence in the mother, decreased quality of life, as well as other bowel problems. There are also possible effects on the infant associated with different modes of delivery. The aim of the BUMPES trial is to evaluate whether a policy of enabling upright position compared to a policy of lying down amongst nulliparous women with a low dose epidural who enter second stage decreases the incidence of IVD and increases the incidence of SVD.

The economic evaluation of the BUMPES trial will evaluate the health care costs and quality of life of women randomised to an upright or lying down position in the second stage of labour with an epidural, up until one year after birth. Therefore, we aim to evaluate whether one position compared to the other one is associated to improvements in quality of life or savings to the National Health Service (NHS) therefore representing value for money of scarce resources.

## 1. The BUMPES Randomised Controlled Trial

Full details of the primary and secondary objectives of the BUMPES study, trial design, eligibility, and so on can be obtained from the main study protocol and the statistical analysis plan study that are available in separate documents. Briefly, BUMPES is a pragmatic multicentre randomised controlled trial (RCT) assessing the effectiveness of: 1) an upright maternal position (intervention group) which would maintain the pelvis in a vertical plane as possible; and 2) a lying down maternal position (control group) which would maintain the pelvis in a horizontal plane as possible. Both interventions begin during the second stage of labour with the intention of continuing the allocated position up until the birth. The BUMPES study will evaluate postnatal maternal and neonatal morbidity and well-being assessed one year after birth.

## 2. The BUMPES Economic Evaluation

### 3.1 Objective of the BUMPES Economic Evaluation

A summary of the components of the BUMPES economic evaluation is presented in Table 1. The BUMPES economic evaluation will compare the cost-effectiveness of upright and lying down positions for women at the start of care in the second stage of labour up to one-year follow-up. The primary health outcome measure for the economic evaluation will be quality-adjusted life-years (QALYs). The results of the cost-effectiveness analysis will be expressed as cost per QALY gained.

**Table 1: Summary of the BUMPES economic evaluation**

Summary	Description
Health Outcome	Maternal Quality Adjusted Life Years (QALYs)
Cost	Delivery procedure costs, original hospital admissions, readmissions, health care visits (for mother and babies)
Timeframe	1 year (12 months) follow-up after birth
Data	Approx. 1,500 women (750 women in each arm)
Data collection	Data collection booklet and maternal questionnaire at one year after birth
Analysis	Intention to treat analysis
Cost-effectiveness results	Cost per QALY gained

### 3.2 Data collection

Around the time of birth, patient-level data will be extracted from the data collection booklet as well as any higher level of care forms for the woman and/or infant who receive a higher level of care. One year follow-up data will be obtained by questionnaire completed by all women whose babies are alive. The questionnaire contains questions on general health and well-being, with specific questions related to any urinary and bowel problems. The questionnaire also collects health care resource use for both mother and infant. There are no further follow-ups in the trial.

### 3.3 Health care resource use data

Tables 2 and 3 detail the specific resource use identified in the BUMPES study, from second stage of labour to hospital discharge (Table 2) and at one-year follow-up (Table 3). Resource use will be collected for both mothers and infants. Note there are no intervention costs for the trial since the trial is of position during labour, which does not have any resources associated to implementation. The resource use included in these tables have been carefully examined by the BUMPES team and revised iteratively. The resource use shaded in grey in Table 2 will not be used for purposes of the economic evaluation as they are already incorporated as part of procedure costs associated to mode of delivery. The economic evaluation will be conducted from a NHS health service perspective and therefore only direct costs to NHS providers will be included. Data on primary and community care visits were not collected alongside the study. We did not want the questionnaire to be too arduous for the woman to complete and we were concerned that these visits, which tend to be less frequent than secondary care visits, would be subject to extensive recall bias. It was also agreed that hospital care would be the main cost driver. However, given that some women in the study may have had symptoms of incontinence for which they may have visited their General Practitioner (GP) and received treatment, we will use section three of the one year-questionnaire which asks about the health of the women to ascertain the proportion that would have been likely to have seen their GP. Data on the proportions of women seeing their GP with specific urinary and faecal incontinence issues will be obtained from research already published in this field by one of the co-investigators of the BUMPES trial ([name]).

**Table 2: Resource use and unit cost measurement from second stage of labour to hospital discharge (all costs to be valued in pounds sterling, 2014 prices)**

Resource use variable	Cost implications	Source of unit cost	Cost valuation/comments	Section of data collection booklet
Maternal details after study entry:				
Epidural technique (epidural/combined spinal or epidural)	Cost of drugs	BNF	Requires looking at pump readings before and afterwards (caveat: missing pump readings)	1.12 & 2.1
Fetal blood sampling	Cost of sampling	NHS	May be different between the arms	2.3
Fetal scalp electrode	Cost of clip	NHS	May be different between the arms	2.4
Drugs for hypotension	Cost of drug (note that no drug recorded)	BNF	May be different between the arms	2.6 & 2.7
Mode of birth	Spontaneous vaginal delivery/assisted delivery/c-section	Reference costs	-	3.3
Primary indication for assisted birth	Cost of assisted by category	NA	No differential staffing so no need to cost	3.4
Anaesthesia required for instrumental birth or c-section (this is in addition to routine epidural pain relief)	Cost of drug	NA	No need to cost – cost will be captured already in reference costs for instrumental births or C-sections	3.5
Active management of third stage labour	Cost of staffing	NA	No differential staffing so no need to cost	3.6
Episiotomy and perineal tear (not counted if woman underwent a c-section)	Cost of episiotomy	Reference costs	Whether the tear was sutured or not is only what is required for costing purposes. Second degree tears will be sutured in the labour ward, whereas suturing of third degree tears will be performed in theatre.	3.7, 3.8, 3.9, 3.10
Manual removal of the placenta	Cost of staff and equipment	Schroeder L, Birthplace costing	£689.32 (2009 cost) -In theatre – needs to be costed separately if a SVD as it will include additional staff, obstetrician, anaesthetist, midwife, and HCA. Does not require costing if	3.11

			woman has had a C-section	
Post-partum haemorrhage requiring transfusion	Cost of PPH & transfusion	Previous NPEU research	-	3.12
Woman admitted to a higher level of care (HDU, ICU) and duration of stay	High dependency care	Reference costs	-	3.14
Infant details:				
Cord blood sampling	Cost of sampling	TBD	Needs to be costed because could represent differences between the arms	3.19
Meconium stained liquor	Additional staff or procedures involved	NA	No differential staffing so no need to cost	3.20
Neonatal resuscitation required at delivery	Resuscitation at birth	Schroeder L, Birthplace costing	£747.77 (2009 cost)	3.21
Infants destination after birth and duration of stay	Higher level neonatal hospitalisation	Reference costs	-	3.24

**Table 3: Resource use and cost data collection at one year for the woman and infant**

Resource use variable	Resource use identified	Source	Comments
Mother details:			
Hospital admission (reason and duration)	Cost of admission multiplied by duration	Reference costs	Will be the most representative costing figure – by classification of reason for admission or ward stay
Operation undergone	Cost of operation	Reference costs	-
Outpatient clinic attended and number of times: Perineal care clinic; Gynaecological; Surgical Other	Cost of clinic attended	Reference costs	Note, need to check data entered as one (first) visit is costed differently to subsequent visits
Infant details:			
Hospital admission (reason and duration)	Cost of admission multiplied by duration	PSSRU	-
Operation undergone	Cost of operation	Reference costs	-
Outpatient clinic attended and number of times: Orthopaedic; Paediatric Hearing; Eye; Dermatology Other	Cost of clinic attended	PSSRU	-

### 3.4 Unit cost data collection

As can be seen in Table 2, where necessary, we have captured items in disaggregated units where we believe the resource use is intervention-related and that a more detailed costing approach will be required. We have in some cases used costing data derived from other studies, whereby clinical experts (clinicians/midwives) document the staffing, medications and equipment, used in the treatment of haemorrhage for example. In these cases, clinical experts were sent a micro-costing sheet to complete with their own resource components. This has comprehensively captured all resource components that might be used.

Unit costs related to health care professionals and services will be derived from national data sources (NHS reference costs or Personal Social Services Research Unit (PSSRU) costs) (Table 3). Reference costs are the average unit cost to the NHS of providing secondary healthcare to NHS patients whereas PSSRU provides salaries for a range of health care professionals.

### 3.5 Maternal quality of life

There is a lack of quality of life measurement scales specifically relevant for use in the maternal and postnatal context. In addition, the possible impact on quality of life on the infant is also of importance but there is no methodological consensus in the literature about how to combine mother/infant utilities data in practice. Using the QALY concept in a paediatric population is

controversial and more research is needed before a framework can be recommended. Therefore, our QALY analysis will only include maternal quality of life.

Maternal quality of life will be derived from the EQ-5D and SF-12 instruments collected in the one-year questionnaire. In pregnant women, the most frequently cited quality of life tool has been the SF-36 (the 36-item version of the SF-12). Similarly to the EQ-5D, SF-12 data can be converted into utilities using the validated SF-6D algorithm. Previous generic research by Petrou and Hockley has provided evidence that the SF-6D is an empirically valid and efficient alternative multi-attribute utility measure compared to the EQ-5D. In particular, they showed that the SF-6D is more efficient than the EQ-5D at detecting differences in self-reported health status, and differences in illness, disability or infirmity and medication use. However, since the EQ-5D is the recommended outcome measure for economic evaluations by National Institute for Health Care Excellence (NICE), we will report the EQ-5D as our main outcome measure in the economic evaluation. We will use information from the SF-12 as a secondary outcome.

Since we did not measure maternal quality of life at the start of randomisation, we will identify relevant studies reporting quality of life about the short-term quality of life implications of the mode of delivery and subsequent complications using a literature search. Evidence from reviews in the area suggests that there are not many studies reporting the relevant information we require. Such estimates will be used for the baseline values for each woman in the QALY calculation.

### 3.6 Analytical methods

The economic evaluation will take the form of a within-trial analysis using patient-level data. In line with the main statistical analysis plan, women contributing data will be analysed using intention-to-treat analysis.

NHS volumes of resource use will be multiplied by the corresponding unit cost to estimate the cost per women for each particular category. The total cost per women will be estimated adding the cost of each category up that allows the calculation of mean cost per women for each trial arm. Recent evidence suggests that both parametric and non-parametric methods accurately estimate the true standard errors even when data are highly skewed and moderate to large ( $n > 50$ ) sample sizes. Hence, mean differences and associated uncertainty for particular categories of resource use and costs between the two positions during the late stage of labour will be estimated using parametric methods.

Utilities associated to a particular health state from the EQ-5D instrument, will be estimated using the UK value set. To derive the QALY profile for each woman in the trial between baseline and one year follow-up we will use a linear straight-line interpolation between assessments in the base case. Other assumptions about connecting the two points (e.g. quality of life changed at midpoint between assessment points) will be evaluated in a sensitivity analysis. We acknowledge that the choice of base case will likely pick up the longer term wellbeing effects that are still evident at 12 months. However it is the severe and persistent forms of urinary and faecal incontinence, and the impact on health related quality of life, that are evident at one year that is of primary importance to the BUMPES trial. We will also estimate the QALY profile for each woman using SF-6D utilities in a sensitivity analysis to evaluate the robustness of the base case QALY results. Mean differences and associated uncertainty in utilities between the intervention groups will be assessed using parametric methods.

A descriptive analysis will provide information about how serious is the presence of missing data in resource use, costs and utilities at one-year follow-up. The decision to impute or not missing data and what exactly to impute will be based on current guidance. If imputation techniques need to be implemented, we will use multiple imputation with chained equation methods and will attempt to impute all components in the economic evaluation. However, this may not be possible due to the

amount of missing data and type of model used and at minimum costs and QALYs will be included in the imputation model. We will combine the statistics of interest (e.g. means and standard errors in each group) using appropriate Rubin rules.

Uncertainty around the cost per QALY gained will be expressed calculating 95% confidence interval around the incremental cost-effectiveness ratio (if appropriate) and using cost-effectiveness acceptability curves (CEACs). We will also present the results of the cost-effectiveness analysis using the net benefit statistics. A full parametric approach will be used to derive ICER's confidence intervals and CEACs. We may implement a bootstrap method to estimate pairs of mean costs and QALYs for each intervention to present uncertainty around cost-effectiveness results using the cost-effectiveness plane.

We will discuss with the clinical team whether cost-effectiveness is likely to vary for a particular subgroup(s) of women and will derive cost-effectiveness results for such subgroups. The subgroup analysis will follow the same methods as the primary analysis.

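### The straight line from birth to 12 months gives a short-term literature utility half a year's weight, and the one sensitivity path the plan names cannot detect this

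*Combined protocol and SAP*

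**What the plan says.** QALYs are the primary health outcome of the economic evaluation (section 3.1), over a horizon of "1 year (12 months) follow-up after birth" (Table 1).

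Utility is measured once: "Maternal quality of life will be derived from the EQ-5D and SF-12 instruments collected in the one-year questionnaire" (section 3.5). Section 3.2 adds: "There are no further follow-ups in the trial".

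The first point of the profile is external. Section 3.5 begins "Since we did not measure maternal quality of life at the start of randomisation" and goes on to say that studies will be sought on "the short-term quality of life implications of the mode of delivery and subsequent complications using a literature search". The estimates found become each woman's baseline value. The same section warns that few studies report what is needed. No utility value and no duration of loss is given.

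Section 3.6 joins the two points: "between baseline and one year follow-up we will use a linear straight-line interpolation between assessments in the base case". It promises sensitivity analyses with other ways of connecting them and gives one example, a change in quality of life at the midpoint. It also concedes that "the choice of base case will likely pick up the longer term wellbeing effects that are still evident at 12 months", and says that lasting, severe incontinence at one year is what matters most to the trial.

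**The concern.** The plan itself describes the starting value as short-term, yet a single line to 12 months lets it fade only over the whole year. A problem present from birth and still present at one year is fully counted only if the published birth value already includes it. The plan gives such problems the highest priority.

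This need not cancel between arms. The Background says the trial tests whether position changes the rate of instrumental and spontaneous birth. If the birth value differs by mode of delivery, as section 3.5 implies, the incremental QALY becomes half an arm difference in delivery outcomes multiplied by external utilities, plus half an arm difference in measured EQ-5D. If every woman were given one common birth value, the first half would cancel, but the measured difference would still be halved.

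At stake is the denominator of the cost per QALY. The expected QALY differences are small, so the weighting can matter for both their size and their sign.

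**Working it through.** The plan states no QALY figure, so there is none to reproduce. The check is the area under the utility curve over one year.

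**Inputs from the plan.** One interval of one year (Table 1); one measured point at 12 months (section 3.5); one literature point at birth (section 3.5); a straight line between them (section 3.6). Write d0 for the utility loss assigned at birth and d1 for the loss at 12 months.

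**Assumed, because the plan gives none.** Duration w of the short-term loss, in weeks; its shape (constant then resolved, or recovering linearly); and all decrements and arm differences in step 4.

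**Step 1: weights under the base case and the named alternative.** Straight line: loss = 0.5 × d0 + 0.5 × d1. Step change at the midpoint: d0 for half a year, then d1 for half a year, so again loss = 0.5 × d0 + 0.5 × d1. The two rules give the same QALY for every woman.

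**Step 2: short-term loss.** A loss of w weeks should carry w/52 year if constant, or w/104 year if it recovers linearly. The ratio of the line's weight to this is 0.5/(w/52) = 26/w, or 0.5/(w/104) = 52/w.

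| Assumed w (weeks) | Constant: weight | Ratio | Linear recovery: weight | Ratio |
|---|---|---|---|---|
| 2 | 0.038 | 13.0 | 0.019 | 26.0 |
| 6 | 0.115 | 4.33 | 0.058 | 8.67 |
| 13 | 0.250 | 2.00 | 0.125 | 4.00 |
| 26 | 0.500 | 1.00 | 0.250 | 2.00 |
| 39 | 0.750 | 0.67 | 0.375 | 1.33 |
| 52 | 1.000 | 0.50 | 0.500 | 1.00 |

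The line is exact for a constant loss of 26 weeks or a linear recovery over 52 weeks. It understates a constant loss that lasts longer than 26 weeks.

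**Step 3: persistent loss.** Suppose a loss is present all year and the assigned birth value carries a share c of it. The line counts (c + 1)/2 of the true loss: 50% for c = 0, 75% for c = 0.5, 100% for c = 1.

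**Step 4: both together.** Illustrations only, with w = 6, constant short-term loss and c = 0. Differences in loss are lying down minus upright, so a positive result favours upright.

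- Offsetting: short-term difference 0.05 × 0.10 = 0.005, persistent difference 0.05 × 0.10 = 0.005. Line: 0.0025 + 0.0025 = 0.0050 QALY. Time-limited short-term loss plus full-year persistent loss: 0.005 × 6/52 + 0.005 = 0.0056. Ratio 0.90.
- Sign change: short-term difference 0.005, persistent difference −0.03 × 0.10 = −0.003. Line: 0.0025 − 0.0015 = +0.0010 QALY. Time-limited plus full-year: 0.0006 − 0.0030 = −0.0024.

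**The case against.** Linear interpolation is a standard method, and with one measured point no path can be verified from trial data. Section 3.5 gives no duration for the short-term effects, and the Background says that operative birth can have profound longer-term consequences. A 6-week recovery is therefore a reviewer's assumption. The literature search also covers later complications, so the birth values may already carry part or all of a persistent loss. The plan openly acknowledges its choice of base case and promises other paths. Any replacement profile rests on external recovery times from a thin literature.

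Most of this stands, and it limits the point. A reader might infer that the base case is simply wrong, that the delivery effect is inflated several-fold, or that the cost per QALY will be driven by a transient effect. The documents support none of these. The inflation depends on a recovery time they do not give, the halving depends on what the birth values contain, and the two errors can offset. Nor does the plan claim that persistent effects receive full weight. Its statement that the base case picks up effects present at 12 months is true as far as it goes; it does not say that those effects may be counted at half.

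The promise of sensitivity analyses does not remove the gap. The only path named has the same weights as the base case, and although it is offered as an example, no other is specified. The SF-6D analysis changes the instrument, with no different path stated. The confidence intervals, acceptability curves and optional bootstrap describe sampling uncertainty, not the choice of path.

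**Conclusion.** The concern holds in conditional form. The equal weights of 0.5 year follow directly from the plan. The short-term loss is over-weighted unless it recovers linearly over about a year or remains constant for about 26 weeks: 4.3- to 8.7-fold at an assumed 6 weeks and 2.0- to 4.0-fold at an assumed 13 weeks. A loss that persists from birth is counted at 50% to 100%, depending on how much of it the birth value carries. The size and direction of the net error in the arm difference cannot be fixed from the documents.

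One part needs no assumption about recovery. Read as a step change, the midpoint alternative is algebraically identical to the base case over a single interval. It would report robustness without testing anything.

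**What to change.** Pre-specify in section 3.6 a profile that applies the delivery and complication decrement only for the recovery time w reported in the source studies, and uses the trial's own 12-month EQ-5D for the rest of the year. With u0 the birth value and u12 the 12-month value:

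- constant, then resolved: QALY = (w/52) × u0 + (1 − w/52) × u12
- linear recovery: QALY = (w/104) × u0 + (1 − w/104) × u12

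Preferably make this the base case and keep the straight line as a sensitivity analysis; this fits the plan's stated priority better. Report it over a range of durations, for example 2 to 26 weeks, because the literature is thin. The constant form at 26 weeks reproduces the present base case, so the range shows how far the result depends on this choice. At minimum, replace the midpoint example with this profile. State also whether the birth values are meant to include complications expected to persist.

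The cost is SAP wording, a few lines of code, and one more item to extract in the literature search already planned. There are two small downsides. The recovery time is an external assumption. The 12-month value is carried back to the end of the recovery period, which backdates any later illness and omits residual loss in women who recovered in between. The profile also does not fully restore a persistent loss that the birth value omits: at 6 weeks, in the constant form, it counts 46/52 = 88% of it, against 50% under the straight line.

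### The only alternative QALY profile named in section 3.6, a change at the midpoint, gives the same QALY as the straight-line base case for every woman

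*Combined protocol and SAP*

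**What the plan says.** Section 3.6 (Analytical methods) fixes the base case: "we will use a linear straight-line interpolation between assessments in the base case". It then commits to checking that choice: "Other assumptions about connecting the two points (e.g. quality of life changed at midpoint between assessment points) will be evaluated in a sensitivity analysis". No other profile is described anywhere in the document.

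The two points are set out elsewhere:

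- **One year (u1).** Section 3.5: "Maternal quality of life will be derived from the EQ-5D and SF-12 instruments collected in the one-year questionnaire". EQ-5D is the main measure. SF-6D utilities, derived from the SF-12, are a sensitivity analysis.
- **Baseline (u0).** Section 3.5 says utility was not measured at randomisation. Values will be sought in published work on mode of delivery and its complications: "Such estimates will be used for the baseline values for each woman in the QALY calculation".
- **Interval.** Table 1 gives the timeframe as "1 year (12 months) follow-up after birth". Section 3.2 describes one questionnaire, at one year. No utility measurement between birth and one year is described.

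Section 3.6 also acknowledges that the base case tends to capture effects lasting to 12 months, and says that serious, lasting incontinence at that time is what matters most to the trial.

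**The concern.** The trial data cannot show how utility moves between birth and 12 months, so the shape of the curve is an assumption. The shape sets how much weight the QALY puts on u0, which is imported from a literature that section 3.5 itself describes as thin, and how much on u1, which is measured. A sensitivity analysis of the shape is useful only if it changes that weight.

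The one example in the plan appears not to change it. If so, the stated check on the interpolation has no ability to show sensitivity, whatever the data. An analyst could run it alone, comply with the plan and obtain identical results, and a reader could take the agreement as evidence that the shape does not matter.

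**Working it through.** The plan states no figure on this point to reproduce, so the check is algebraic.

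**Inputs.** Two utility points, u0 and u1 (sections 3.5 and 3.6); interval T = 1 year (Table 1); base-case profile a straight line (section 3.6); named alternative a change at the midpoint (section 3.6), read as one step from u0 to u1 at 6 months.

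**Step 1: the identity.**

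- Straight line: QALY = T(u0 + u1)/2 = 0.5·u0 + 0.5·u1.
- Step at time w, as a fraction of the year: QALY = w·u0 + (1 − w)·u1.
- At the midpoint, w = 0.5: QALY = 0.5·u0 + 0.5·u1, the same expression.

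Examples: (u0, u1) = (0.6, 0.9) gives 0.750 under both; (0.9, 0.7) gives 0.800 under both; (−0.594, 1) gives 0.203 under both. The result does not depend on arm, value set or instrument, so it holds for SF-6D as well as EQ-5D. Because each woman's QALY is unchanged, so is everything calculated from it.

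**Step 2: what a different shape would do.** Let d0 and d1 be the between-arm utility differences at baseline and one year. The incremental QALY is w·d0 + (1 − w)·d1, and its departure from the base case is (w − 0.5)(d0 − d1). This is zero if w = 0.5 or if d0 = d1.

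The values of d0 and d1 below are assumptions, chosen only to illustrate:

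| Profile | Weight w on u0 | d0 = 0.05, d1 = 0.01 | d0 = 0.02, d1 = 0 | d0 = d1 = 0.03 |
|---|---|---|---|---|
| Straight line (base case) | 0.50 | 0.030 | 0.010 | 0.030 |
| Step at midpoint (named example) | 0.50 | 0.030 | 0.010 | 0.030 |
| Step at 6 weeks | 6/52 = 0.115 | 0.0146 | 0.0023 | 0.030 |
| Step at 3 months | 0.25 | 0.020 | 0.005 | 0.030 |
| Step at 9 months | 0.75 | 0.040 | 0.015 | 0.030 |

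For the first pair, the 3-month step is 0.25 × 0.05 + 0.75 × 0.01 = 0.020 and the 9-month step is 0.75 × 0.05 + 0.25 × 0.01 = 0.040. Where d1 = 0 and the cost difference is held fixed, the ICER is multiplied by 0.5/w: 2 for the 3-month step and about 0.67 for the 9-month step.

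**Step 3: check on simulated data.** Two arms of 750 (the approximate arm size in Table 1) were simulated with assumed utilities. The largest difference for any woman between the straight line and the midpoint step was 0.0. Both gave a mean difference of 0.010265 (SE 0.003499). A 3-month step gave 0.007398 (SE 0.004525) and a 9-month step 0.013133 (SE 0.003130). A profile with another weight can therefore change the standard error as well as the estimate.

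**Step 4: only the weight matters.** Differently drawn profiles with the same w are the same analysis. A linear recovery completed at 12 weeks and flat afterwards has w = (12/52)/2 = 6/52, identical to a step at 6 weeks.

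**The case against.** The strongest reply is that the midpoint change is only an example. The sentence speaks of "Other assumptions about connecting the two points" in the plural, so the commitment is wider than the illustration. That stands: a reader might infer that the whole interpolation sensitivity analysis is void, and the text does not support this. What remains is that no informative shape is specified, so the commitment can be met by the one analysis that cannot differ.

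A second reply concerns the reading of "quality of life changed at midpoint between assessment points". If it meant a linear change that starts or ends at 6 months, the weight on u0 would be 0.75 or 0.25 and the test would be real. The sentence also cites a source that is not available here and may define the profile. The text does not state that meaning, a single step is the natural reading, and the other meaning would itself need the sentence rewritten.

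Third, a reader might infer that the report will claim robustness on this basis. That is a prediction about reporting. Identical results for every woman would be plain to the analyst and might prompt another profile. In section 3.6 the aim of checking robustness is attached to the SF-6D analysis, which tests the instrument and not the shape. The supportable statement is that an unchanged result could be misread.

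Finally, the shape is not shown to be the main unverifiable assumption: the unmeasured baseline is at least as large a candidate. Nor do the documents show that any cost-effectiveness conclusion would change.

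**Conclusion.** The example is wrong as written. Read as a single step at 6 months, it reproduces the base case exactly, so its effect on the incremental QALY, standard error, ICER, net benefit and CEAC is zero for any data. This rests only on there being two utility points and on that reading; it needs no assumption about utilities.

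How much an informative alternative would matter is unknown. The incremental QALY moves only if the between-arm utility difference changes between baseline and one year. That is plausible, since u0 will follow mode of delivery and complications while u1 is measured a year later, but the documents give no utilities and every magnitude shown is illustrative.

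The base-case estimate, the costing and the methods for the ICER and CEAC are unaffected. This is a defect in a secondary analysis that should be fixed before the analysis is run, not one that undermines the economic evaluation.

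**What to change.** In section 3.6, replace the midpoint example with at least two named profiles whose weight on baseline is not 0.5, one below and one above. Steps at 3 months (weight 0.25) and 9 months (weight 0.75) would do. An early-recovery profile such as a step at 6 weeks (weight 0.115) could be added. The documents do not dictate these times; what matters is that the weights differ from 0.5 and from each other. For that reason, do not also include a linear recovery completed by 12 weeks, which duplicates the 6-week step.

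State the baseline weight of each profile, and report the incremental QALY and net benefit for each beside the base case. If a change beginning or ending at 6 months was intended, say so and give its weight.

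The cost is one sentence in the plan and a few lines of code, with no new data.
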